Duration of Subject Participation:	Time between Screening and drug product infusion will be variable and is estimated generally to be between 3 to 5 months (e.g., up to 3 months between Screening and Mobilization, followed by approximately 2 months before drug product infusion). Thereafter the subject is planned to remain on study for approximately 24 months. Eligible subjects are expected to enroll in a separate long-term follow-up study until approximately 15 years post-drug product infusion.
Test Product, Dose and Mode of Administration:	bb1111 is an autologous CD34+ cell-enriched population from patients with sickle cell disease that contains hematopoietic stem cells transduced with BB305 lentiviral vector encoding the $\beta^{\text{A-T87Q}}$ -globin gene, suspended in cryopreservation solution. All subjects are to receive $\geq 3.0 \times 10^6$ CD34 ⁺ cells/kg of bb1111 on Day 1 via intravenous infusion.

Efficacy Endpoints:	
Primary Efficacy Endpoint: VOE-CR, defined as complete resolution of VOEs, between 6 months and 18 months after drug product infusion

	
Key Secondary Efficacy Endpoints:
 
 • sVOE-CR, defined as complete resolution of severe VOEs, between 6 months and 18 months after drug product infusion • Globin Response, defined as meeting the following criteria for a continuous period of at least 6 months after drug product infusion: 
 a. Weighted average HbA^{T87Q} percentage of non-transfused total Hb¹ $\geq 30\%$ AND b. Weighted average non-transfused total Hb¹ increase of ≥ 3 g/dL compared to baseline total Hb² OR weighted average non-transfused total Hb¹ ≥ 10 g/dL
	
Additional Secondary Efficacy Endpoints:
 
Clinical and Disease Evaluation Endpoints:
 
 • Change in the annualized number of VOEs in the 24 months after drug product infusion compared to the 24 months prior to Informed Consent • Change in the annualized number of severe VOEs in the 24 months after drug product infusion compared to the 24 months prior to Informed Consent • VOE-CR24, defined as complete resolution of VOEs, between 6 months and 24 months after drug product infusion • sVOE-CR24, defined as complete resolution of severe VOEs between 6 months and 24 months after drug product infusion • sVOE-75, defined as at least a 75% reduction in annualized severe VOEs in the 24 months after drug product infusion compared to the 24 months prior to Informed Consent 
Characterization of Globin Response:
 
 • Proportion of subjects who meet the definition of Globin Response at Month 24 • Duration of Globin Response 
Hematologic Endpoints:
 
 • Weighted average for the following at Month 6, 12, 18, and 24: 
 – non-transfused total Hb¹ – HbS percentage of non-transfused total Hb¹ – HbS percentage of non-transfused total Hb¹ $\leq 70\%$, $\leq 60\%$, $\leq 50\%$ – HbA^{T87Q} percentage of non-transfused total Hb¹ – non-HbS³ percentage of non-transfused total Hb¹ • Assessment of the following over time:

	
 - non-transfused total Hb¹ - HbS percentage of non-transfused total Hb¹ - HbA^{T87Q} percentage of non-transfused total Hb¹ - non-HbS³ percentage of non-transfused total Hb¹ • Change from baseline in hemolysis markers, including absolute reticulocyte count, % reticulocytes/erythrocytes, total bilirubin, haptoglobin, and lactate dehydrogenase • Change from baseline in markers of iron stores including ferritin, liver iron content, and if assessed at baseline, cardiac iron content • Change from baseline in annualized frequency and volume of packed red blood cell (pRBC) transfusions between 6 months and 24 months after drug product infusion • Change from baseline in markers of stress erythropoiesis, including erythropoietin and serum transferrin receptor 
SCD Burden and Chronic Complications Assessments:
 
 • Change from baseline in renal function as measured by eGFR • Change from baseline in cardiac-pulmonary function via echocardiogram (tricuspid regurgitant jet velocity [TRJV], LVEF) and pulmonary function tests • Change from baseline in meters walked during 6-minute walk test 
Hospitalizations and Quality of Life:
 
 • Change from baseline in annualized VOE-related hospital admissions and days • Change from baseline in patient-reported quality of life, as measured by Patient Reported Outcomes Measurement Information System (PROMIS) 
Exploratory Efficacy Endpoints:
 
 • Change from baseline in cerebral vasculature and prior brain parenchymal injury evaluation at Month 12 and Month 24 (as measured by cerebral magnetic resonance angiography [MRA]/magnetic resonance imaging [MRI] in all subjects, and transcranial Doppler [TCD] for subjects ≤ 16 years old at Informed Consent) • Change from baseline in bone mineral density (BMD) evaluation using dual x-ray absorptiometry (DXA) at Month 24 • Change from baseline in brain natriuretic peptide • Change from baseline in Patient reported Outcome (PRO) measures including: 
 - Overall health: EuroQol-5D (EQ-5D-3L or EQ-5D-Y) - Work productivity, as measured by the Work Productivity and Activity Impairment Questionnaire-General Health (WPAI-GH or Caregiver WPAI-GH) - Cognitive function as measured by PROMIS Short Form 6a • Evaluation of chronic pain using AAPT
--	--

	
 • Change from baseline in pain medication use • Exploratory assays to assess change from baseline in sickle cell characteristics and bone marrow pathophysiology
Pharmacodynamic Endpoints:	
 • Vector copy number (VCN) in peripheral blood over time • Expression of β^{A-T87Q}-globin, β^S-globin, and other β-like-globins in peripheral blood over time 
Additional methods may be used to evaluate pharmacodynamics.

Safety Endpoints:	
Safety will be evaluated by the following:
 
 • Safety and tolerability of plerixafor for mobilization • Success and kinetics of HSC engraftment • Transplant-related mortality through 100 days post-drug product infusion and through 365 days post-drug product infusion • Detection of vector-derived replication competent lentivirus (RCL) in any subject • The number of subjects with insertional oncogenesis (myelodysplasia, leukemia, lymphoma, etc.) • The number of subjects with persistent oligoclonality • Frequency and severity of AEs/SAEs • Laboratory parameters over time, including the following immunology tests: Screening for irregular antibodies, lymphocyte subpopulation evaluation (CD3, CD4, CD8, CD19, CD16/CD56) • Incidence of acute and/or chronic graft-versus-host disease (GVHD) • Other safety labs over time: chemistries, LFTs (AST, ALT, ALP, GGT, bilirubin [total and direct]), hematology, coagulation parameters • Hormonal testing over time: estradiol (females only); total testosterone (males only) TSH, free T3, free T4, cortisol, ACTH, FSH, LH (all subjects) • Change from baseline in methemoglobin concentration at Month 12 and Month 24 • Number of subjects with presence of a chromosomal abnormality or genetic mutation associated with hematologic malignancies over time
Statistical Methods:	
Sample Size Estimation
 
The sample sizes for Group A and B were not determined by formal statistical methods. Approximately 41 subjects will be enrolled in Group C, approximately 35 of whom must meet the severe VOE criteria as set forth in Inclusion Criterion #3.1.
 
Assuming 80% of subjects in Group C who have at least 4 VOEs in the 24 months prior to Informed Consent will meet the primary efficacy endpoint VOE-CR, 35 subjects will provide more than 99% power to reject the null hypothesis of 40% at 1-sided alpha of 0.025, using the Exact Test per EAST® (Version 6). The success criterion is 60% (21 out of 35) of subjects meeting the primary efficacy endpoint, if exactly 35 subjects with at

	
least 4 VOEs in the 24 months prior to Informed Consent are enrolled and received drug product in Group C.
 
Power calculations were also performed for the key secondary efficacy endpoints of sVOE-CR and Globin Response. Assuming 85% of subjects in Group C with at least 4 VOEs in the 24 months prior to Informed Consent will meet sVOE-CR, 35 subjects will provide more than 99% power to reject the null hypothesis of 50% at 1-sided alpha of 0.025, using the Exact Test per EAST® (Version 6); the success criterion is 69% (24 out of 35) of subjects meeting sVOE-CR, if exactly 35 subjects with at least 4 VOEs in the 24 months prior to Informed Consent are enrolled and receive drug product in Group C. Assuming 70% of subjects will meet Globin Response, 41 subjects will provide approximately 96% power to reject the null hypothesis of 40% at 1-sided alpha of 0.025, using the Exact Test per EAST® (Version 6); the success criterion is 59% (24 out of 41) of subjects meeting Globin Response, if exactly 41 subjects are enrolled and received drug product in Group C.
 
Populations for analysis
 
The following subject populations will be evaluated and used for presentation and analysis of the data:
 
• Intent-to-Treat (ITT) Population: All subjects who initiate any study procedures, beginning with stem cell collection procedures (mobilization/apheresis or bone marrow harvest).• Transplant Population (TP): All subjects who receive drug product.• Transplant Population for VOE (TPVOE): Subset of TP subjects with at least 4 VOEs in the 24 months prior to Informed Consent.• Successful Engraftment Population (SEP): A subset of TP subjects who, following busulfan myeloablation and drug product infusion, successfully engraft with drug product, defined as 3 consecutive absolute neutrophil count (ANC) $\geq 0.5 \times 10^9/L$ laboratory values obtained on different days after the initial post-infusion nadir by Day 43. 
The ITT is the primary population for the analysis of safety, the TPVOE is the primary population for VOE-related endpoints including the primary efficacy endpoint of VOE-CR and the key secondary endpoint of sVOE-CR, the TP is the primary population for the key secondary efficacy endpoint of Globin response, and the other secondary efficacy endpoints and pharmacodynamic endpoints. The SEP will be used to provide supportive data for subjects who engraft.
 
Analysis of the primary efficacy endpoint in Group C
 
The primary endpoint of VOE-CR will be tested against the null hypothesis of 40% using a 1-sided exact binomial test. The number and percentage of subjects reaching the primary endpoint will be presented. The associated 2-sided exact 95% confidence interval will be provided. The primary endpoint will be analyzed in the TPVOE population in Group C subjects.
 
Analysis of the key secondary efficacy endpoints in Group C
 
The key secondary endpoint of sVOE-CR will be tested against the null hypothesis of 50% using a 1-sided exact binomial test. The number and

--	--

	
percentage of subjects reaching the endpoint will be presented. The associated 2-sided exact 95% confidence interval will be provided. The endpoint will be analyzed in the TPVOE population in Group C subjects.
 
The key secondary endpoint of Globin Response will be tested against the null hypothesis of 40% using a 1-sided exact binomial test. The number and percentage of subjects reaching the endpoint will be presented. The associated 2-sided exact 95% confidence interval will be provided. The endpoint will be analyzed in the TP in Group C subjects.
 
The planned statistical methodology details will be presented in the Statistical Analysis Plan (SAP).

--	--

¹ Non-transfused total Hb is the total g/dL of HbS + HbF + HbA₂ + HbA^{T87Q}. For subjects with a β^+ allele, HbA will also be included in the calculation of “non-transfused total Hb” only for samples taken ≥ 60 days after last pRBC transfusion.

² Baseline total Hb is defined as follows:

The average of the 2 most recent Hb assessments made at or prior to the Screening evaluation, which meet the following criteria:

- (i) Assessments must be separated by at least 1 month from each other.
- (ii) Assessments must have been drawn no earlier than 24 months prior to Informed Consent and may include the Hb result from Screening.
- (iii) The subject will not have received a pRBC transfusion within 3 months prior to each Hb assessment.

For subjects who are on chronic, recurrent transfusions, and do not have 2 Hb assessments which meet criteria (i), (ii), and (iii), the following criteria can be used: 2 Hb values which meet criteria (i) and (iii) that are found within 24 months prior to the start of a regular transfusion program.

³ Non-HbS is the total g/dL of HbF + HbA₂ + HbA^{T87Q}. For subjects with a β^+ allele, HbA will also be included in the calculation of “non-HbS” only for samples taken ≥ 60 days after last pRBC transfusion.

LIST OF ABBREVIATIONS

Abbreviation	Definition
6MWD	the distance that a patient can quickly walk on a flat, hard surface in a period of 6 minutes
6MWT	six-minute walk test
ACS	acute chest syndrome
AE	adverse event
allo-HSCT	allogeneic hematopoietic stem cell transplantation
ALP	alkaline phosphatase
ALT	alanine aminotransferase
AML	acute myeloid leukemia
ANC	absolute neutrophil count
aPTT	activated partial thromboplastin time
AST	aspartate aminotransferase
AUC	area under the curve
BMD	bone mineral density
BNP	brain natriuretic peptide
CBC	complete blood count
CKD-EPI	Chronic Kidney Disease Epidemiology Collaboration
CMV	cytomegalovirus
CRE	conditioning-related events
CRF	case report form
CRP	C-reactive protein
DL _{CO}	carbon monoxide diffusing capacity
DLT	dose limiting toxicities
DMC	Data Monitoring Committee
DNA	deoxyribonucleic acid
DXA	dual x-ray absorptiometry
EBV	Epstein-Barr virus
EC	Ethics Committee
EFS	event-free survival
EU	European Union
eGFR	estimated glomerular filtration rate
FDA	Food and Drug Administration

Abbreviation	Definition
FEV ₁	forced expiratory volume in 1 second
FISH	fluorescence in situ hybridization
FSH	follicle stimulating hormone
FVC	forced vital capacity
GCP	Good Clinical Practice
G-CSF	granulocyte colony stimulating factor
GFR	glomerular filtration rate
GGT	gamma-glutamyl transferase
GVHD	graft-versus-host-disease
Hb	hemoglobin
HbA	hemoglobin A, that contains β-globin
HbA ₂	hemoglobin A ₂ , that contains δ-globin
HbA ^{T87Q}	HbA, that contains β ^{A-T87Q} -globin
HBcAb	hepatitis B core antibody
HbF	hemoglobin F, that contains γ-globin
HbS	hemoglobin S, that contains β ^S -globin
HBsAb	hepatitis B surface antibody
HBsAg	hepatitis B surface antigen
HCV	hepatitis C virus
HIV	human immunodeficiency virus
HIV-1	human immunodeficiency virus type 1
HIV-2	human immunodeficiency virus type 2
HLA	human leukocyte antigen
HPC-A	hematopoietic progenitor cells obtained by apheresis
HPLC	high-performance liquid chromatography
HSC	hematopoietic stem cell
HSCT	hematopoietic stem cell transplantation
HSV	herpes simplex virus
HTLV-1	human T lymphotropic virus 1
HTLV-2	human T lymphotropic virus 2
HU	hydroxyurea
ICF	informed consent form
ICH	International Council for Harmonisation

Abbreviation	Definition
IEC	Independent Ethics Committee
INN	international nonproprietary name
IRB	Institutional Review Board
IS	insertion site
ISA	integration site analysis
ITT	intent-to-treat
IV	intravenous
LCR	locus control region
LDH	lactate dehydrogenase
LH	luteinizing hormone
LVEF	left ventricular ejection fraction
LVV	lentiviral vector
MDS	myelodysplastic syndrome
MedDRA	Medical Dictionary for Regulatory Activities
MRA	magnetic resonance angiography
MRI	magnetic resonance imaging
MSD	matched-sibling donor
NGS	next generation sequencing
OS	overall survival
PBLs	peripheral blood leukocytes
PCR	polymerase chain reaction
PD	pharmacodynamics
PFTs	pulmonary function tests
PI	Principal Investigator
PK	pharmacokinetics
pRBC(s)	packed red blood cell(s)
PRO	Patient-reported Outcome

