--	---

	
27. Patients needing therapeutic anticoagulation treatment during the period of conditioning through platelet engraftment (patients on prophylactic doses of anticoagulants not excluded per this criteria).
 
28. Unable to receive RBC transfusion.
 
29. Any other condition that would render the subject ineligible for HSCT, as determined by the attending transplant physician.
 
30. Applicable to subjects < 18 years of age only: Availability of a willing, matched HLA-identical sibling hematopoietic cell donor.

Concomitant Medications/Therapies:	Subjects will be permitted to take their usual medications during the study, with the following exceptions: erythropoietin, which should be discontinued 60 days prior to stem cell collection; HU, which should be discontinued 30 days prior to HSC mobilizations and collections; and iron chelation therapy, which should be discontinued at least 7 days prior to conditioning. Hydroxyurea may be restarted between completion of the stem cell harvest(s) and admission to the hospital for myeloablation but should be stopped again at least 2 days before initiating myeloablation. In case of iron overload, subjects should be adequately chelated; however, iron chelation must be discontinued at least 7 days prior to stem cell harvest. Phlebotomy or iron chelation therapy may be restarted no sooner than 3 months after transplant. Subjects should not use medications with anti-retroviral activity (such as those used for HIV prophylaxis) from within 1 month of initiating mobilization until after completion of stem cell collection for drug product manufacture. Blood products will be filtered and irradiated, as needed. Management of post-transplant transfusions for subjects with SCD will follow the institutional standard of care at the clinical site to achieve total Hb and HbS proportions appropriate for each subject's clinical status. To achieve this, the transfusion program may be progressively reduced as the contribution of hemoglobin containing $\beta^{\text{A-T87Q}}$ -globin rises. Continued transfusion needs > 6 months post-treatment or any alternative plans should be discussed with the Medical Monitor. Following HSC transplant, medications other than blood transfusions to treat sickle cell disease or anemia (e.g., HU, erythropoietin, L-glutamine, crizanlizumab, voxelotor) are not permitted without prior discussion with and explicit approval of the Sponsor's Medical Monitor.

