Anti-seizure prophylaxis must begin at least 12 hours before initiating busulfan and must continue for at least 24 hours after completion of the 4 days of busulfan administration. All drugs other than phenytoin are allowed for anti-seizure prophylaxis.

After completion of the 4-day course of busulfan, there must be a minimum of 48 hours before drug product infusion. Busulfan levels will be measured 48 and 72 hours after final dose of busulfan for retrospective confirmation of adequate wash-out.

On Day 1, bb1111 will be administered after thawing via IV infusion.

Stage 4 – Follow-up, for approximately 24 months after drug product infusion

Subjects will be followed in the hospital for AEs, and laboratory parameters will be followed to monitor engraftment. The subject may be discharged after neutrophil engraftment occurs ($\geq 0.5 \times 10^9$ ANC/L for 3 consecutive measurements on different days after the initial post-infusion nadir) and the subject is considered medically stable per institutional guidelines.

From drug product infusion through hospital discharge after neutrophil engraftment, subjects are to be medically managed with the goal of maintaining the following hematologic targets:

- Hb 8 to 10 g/dL (not to exceed 12 g/dL), HbS $< 30\%$ and
- platelet count $\geq 50 \times 10^9/\text{L}$.

After discharge, management of transfusions for subjects with SCD will follow the institutional standard of care at the clinical site to achieve total Hb and HbS proportions appropriate for each subject's clinical status. To achieve this, the transfusion program may be progressively reduced

as the contribution of Hb containing $\beta^{\text{A-T87Q}}$ -globin rises. Continued transfusion needs > 6 months post-treatment or any alternative plans should be discussed with the Medical Monitor.

Subjects will be followed in this protocol through the Month 24 Visit. Thereafter, subjects are expected to enroll in a separate, non-interventional, long-term follow-up protocol that will assess safety and efficacy beyond Month 24 for a total of 15 years after drug product infusion. The end of Study HGB-206 will be defined as the last visit for the last subject.

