4. STUDY POPULATION

4.1. Number of Subjects

A total of approximately 50 subjects will be treated with bb1111 in Study HGB-206.

Seven subjects have already been treated in Group A, and 2 subjects have been treated in Group B. A total of approximately 41 subjects in Group C (including subjects consented under Versions 7.0, 8.0, and 9.0 of this protocol) will be treated with bb1111, approximately 35 of which must meet the severe VOE criteria as set forth in Inclusion Criterion #3.1.

Subjects who withdraw prior to drug product infusion may be replaced.

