5.8.2. Concomitant Medications and Therapies

All concomitant medications and therapies (i.e., those that are taken by the subject after signing the informed consent form [ICF]) should be documented.

Instructions and/or restrictions regarding specific concomitant medications and therapies are listed below. Concomitant medications and therapies not explicitly listed below may be used at the discretion of the treating physician and as per local standard of care.

- Granulocyte colony stimulating factor (G-CSF): G-CSF should not be used prior to Day 43 without explicit approval from the bluebird bio Medical Monitor.
- Venous access: Subjects will have appropriate long-term central venous access placed, per institutional standard practice, prior to beginning the preparative regimen. For subjects planned to undergo apheresis, placement of central venous access prior

to the first dose of plerixafor is strongly advised. For access, a double lumen tunneled catheter is recommended.

- Hydroxyurea: Hydroxyurea must be discontinued at least 30 days prior to stem cell harvest. It may be restarted between completion of the stem cell harvest(s) and admission to the hospital for myeloablation but should be stopped again at least 2 days before initiating myeloablation. Following HSC transplant, HU is not permitted without prior discussion with and explicit approval of the Sponsor's Medical Monitor.
- Erythropoietin: Erythropoietin is excluded and must be discontinued 60 days prior to stem cell harvest, as it may prevent engraftment of the transduced cells. Following HSC transplant, erythropoietin is not permitted without prior discussion with and explicit approval of the Sponsor's Medical Monitor.
- L-glutamine, crizanlizumab, and voxelotor: Following HSC transplant, medications other than blood transfusions to treat sickle cell disease or anemia (e.g., HU, erythropoietin, L-glutamine, crizanlizumab, voxelotor) are not permitted without prior discussion with and explicit approval of the Sponsor's Medical Monitor.

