- Iron chelation therapy: Iron chelation therapy must be discontinued at least 7 days prior to stem cell harvest and conditioning. Phlebotomy or iron chelation therapy using deferasirox or deferoxamine may be restarted at the discretion of the treating physicians no sooner than after discharge from the hospital post-transplant. Deferiprone use is not permitted without prior discussion with and explicit approval of the Sponsor's Medical Monitor. Deferiprone may be used no sooner than 3 months after transplant due to the potential risk of myelosuppression (as per prescribing information for Deferiprone).
- Seizure prophylaxis: Starting at least 12 hours prior to the first dose of busulfan for conditioning, subjects will be treated with anticonvulsants for seizure prophylaxis. The choice of anticonvulsant is at the discretion of the treating physician, but phenytoin is not allowed. Seizure prophylaxis can be discontinued 24 hours after the last dose of busulfan.
- Subjects should not use medications with anti-retroviral activity (such as those used for HIV prophylaxis) from within 1 month of initiating mobilization until after completion of stem cell collection for drug product manufacture.
- pRBC Transfusions: A transfusion regimen will be implemented for at least 60 days before stem cell harvest, and will continue through until busulfan conditioning (exchange or simple, as available or needed) to reach a target Hb of 10 g/dL prior to mobilization (and 8 to 10 g/dL prior to conditioning; not to exceed 12 g/dL prior to either mobilization or conditioning) and a pre-transfusion target HbS proportion in the blood of < 30% to reduce the risk of SCD-related complications. The last exchange transfusion must occur within 4 days of start of mobilization (or within 1 week of start of conditioning regimen), and the HbS proportion in the blood must be < 20% after the last exchange transfusion prior to mobilization, and < 30% after the last exchange transfusion prior to conditioning. Hemoglobin S should be quantified

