7.4.2. Disposition of Subjects

A tabulation of the disposition of subjects will be presented, including the number harvested, infused, and the number with any post-drug product infusion data available for analysis, and the extent of data available. Tables and listings will be provided for subjects in each analysis data set, including the distribution of subjects according to genotype. Subject data will also be displayed by site. The number of subjects completing the study through 2 years after drug product infusion and reasons for study discontinuation will be reported. Deviations from protocol treatment and assessment specifications will be tabulated and listed.

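### The synopsis bars phlebotomy and all iron chelation until 3 months after transplant, while Protocol Section 5.8.2 allows phlebotomy, deferasirox or deferoxamine from hospital discharge

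*Protocol*

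**What the plan says.** Under Concomitant Medications/Therapies, the synopsis gives one rule for the period after transplant: "Phlebotomy or iron chelation therapy may be restarted no sooner than 3 months after transplant". It applies to phlebotomy and to every chelator alike.

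Protocol Section 5.8.2 introduces its own list with "Instructions and/or restrictions regarding specific concomitant medications and therapies are listed below". For iron removal it separates the agents:

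- For phlebotomy and two of the chelators: "Phlebotomy or iron chelation therapy using deferasirox or deferoxamine may be restarted at the discretion of the treating physicians no sooner than after discharge", meaning the discharge that ends the transplant admission.
- For deferiprone, a floor with a reason: "Deferiprone may be used no sooner than 3 months after transplant due to the potential risk of myelosuppression". Whenever it is used, the Medical Monitor must also have been consulted and have agreed beforehand.

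Both texts are current; neither comes from the summary of changes. I found no statement in the protocol of which prevails if synopsis and body differ.

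**The concern.** A synopsis may leave out detail, but here it states a prohibition that the body does not contain. A site treating a subject with iron overload, discharged and not yet at 3 months, gets opposite answers on deferasirox depending on which page it reads. If it follows the synopsis, it withholds treatment that Section 5.8.2 leaves to the physician. If it follows Section 5.8.2, its conduct can be written up as a deviation against the synopsis.

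The deferiprone gap is smaller but runs the other way. A reader of the synopsis alone would see a 3-month wait and no approval step, and could start the drug at 3 months without consulting the Medical Monitor. Section 5.8.2 gives myelosuppression as its reason for caution with this drug.

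Protocol Section 7.4.2 says "Deviations from protocol treatment and assessment specifications will be tabulated and listed", so the governing rule should be settled before deviations are coded.

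**Working it through.** The plan gives no figure to reproduce. The check is a comparison of texts, plus one piece of arithmetic on timing.

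**1. Rule by agent**

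| Option | Synopsis | Section 5.8.2 | Match? |
|---|---|---|---|
| Phlebotomy | 3 months | After discharge, physician's discretion | No |
| Deferasirox | 3 months | After discharge, physician's discretion | No |
| Deferoxamine | 3 months | After discharge, physician's discretion | No |
| Deferiprone, timing | 3 months | 3 months | Yes |
| Deferiprone, approval | Not mentioned | Medical Monitor approval required | Omitted |

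**2. Can discharge come before 3 months?** Section 3.1 (Stage 4) permits discharge once neutrophils have engrafted and "the subject is considered medically stable per institutional guidelines". Section 3.4 treats engraftment not reached by Day 43 as failure. Table 4 places Month 3 at Day 90. SAP Section 3.2 defines a month as 30.4375 days, so 3 months = 3 × 30.4375 = 91.3, or 91 days. The last day on which engraftment counts as successful therefore precedes the 3-month point by 90 − 43 = 47 days, or 91 − 43 = 48 days. Medical stability may come later, so this is not the length of the disputed window. It shows only that the window can exist.

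**3. Does other text reconcile the two rules?**

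- The synopsis also has a Medical Monitor clause for drugs used after transplant. It covers treatments for sickle cell disease or anemia, and its examples (HU, erythropoietin, L-glutamine, crizanlizumab, voxelotor) include no chelator. It does not supply the missing deferiprone step.
- Table 4 footnote 9 asks for iron studies before chelation is restarted. The first scheduled post-infusion iron study is at Month 3, which sits more easily with a 3-month floor. But Table 3 schedules iron studies before conditioning, and Section 6.1 allows unscheduled assessments, so the footnote does not rule out an earlier restart.

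**4. What follows in the analysis?** SAP Section 2.2 lists all deviations, counts major ones by group in the ITT population, and fixes the major/minor classification before database lock. SAP Table 2 defines ITT, TP, SEP and TPVOE; there is no per-protocol set. Protocol Section 7.4.4.3 summarizes the iron-store endpoints descriptively. A deviation code therefore removes nobody from any analysis.

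**The case against.** The strongest reply is that this is editorial. A site that waits 3 months, and obtains approval for deferiprone, satisfies both texts. On timing, the synopsis errs on the cautious side. Nothing shows that any restart was logged as a deviation, and the pre-lock review in SAP Section 2.2 already exists to sort such cases. All of this stands, and it keeps the point minor. It does not remove the conflict, because these are treatment rules and one of them forbids what the other permits.

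A second reply is that the sponsor may have meant 3 months for all agents, as the Month 3 iron study could suggest. That remains possible, since the documents state no order of precedence. The better inference is still Section 5.8.2: it is the dedicated list, it distinguishes agents, and it gives a reason for singling out deferiprone. It remains an inference, so the sponsor should confirm it.

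A third reply is that omitting an approval step is ordinary summarizing. That is right. A reader might infer that the two texts contradict each other on deferiprone. They do not: the floor is the same, and the synopsis nowhere says that approval is unnecessary.

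**Conclusion.** The inconsistency on restart timing is real for phlebotomy, deferasirox and deferoxamine. The missing deferiprone approval is a secondary omission. The consequence is limited to what sites do between discharge and 3 months and how those restarts are classified. VOE-CR, sVOE-CR, Globin Response and the power calculations are untouched.

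The size cannot be stated further. A reader might put a length on the window by choosing a typical discharge day, but the documents give none.

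A reader might also subtract the 45 infused subjects in SAP Table 1 (7 + 1 + 1 + 36) from the target in Protocol Section 4.1, "A total of approximately 50 subjects will be treated with bb1111 in Study HGB-206", and conclude that at most 5 subjects could still be affected. The documents do not support that bound. The target is approximate, and the SAP refers to supplementary analyses for the final study report, so the number still to be treated may be zero. In the other direction, the subtraction ignores any infused subject still short of Month 3, and anyone still on study to whom the deferiprone approval step applies.

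The conclusion rests on the current wording of the two sections and on discharge being possible before 3 months.

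**What to change.** 1. The sponsor confirms that the agent-specific rule in Section 5.8.2 governs.
2. Replace the synopsis sentence with that rule: phlebotomy, deferasirox or deferoxamine from post-transplant discharge at the treating physicians' discretion; deferiprone from 3 months, and only with the Medical Monitor's prior approval. Use the next amendment, or a clarification memo if none is planned.
3. Add to Table 4 footnote 9 that an unscheduled iron study is needed if chelation restarts before Month 3.
4. In the existing pre-lock deviation review, classify related deviations against Section 5.8.2. Do not apply a 3-month floor to all agents retrospectively, since that would turn conduct the body permitted into deviations.

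The cost is two sentences in the synopsis, one clause in a footnote and one line in the deviation-review record. Recruitment and the scheduled visits stay as they are. The only added test would be an iron study for a subject who restarts chelation before Month 3.
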